5.7.2 Handling of Participant Withdrawals or Termination

Patients who withdraw or terminate participation in this study will be called and a follow-up office visit will be set up at 12 weeks regardless of their participation. If the patient refuses to come in, a phone call will be made to discuss adverse events or unanticipated problems over the phone. If a patient is lost to follow-up, two phone calls to the patient and subsequently two phone calls to next-of-kin will be made in an attempt to reach the patient. There is low concern for long-term and short-term safety with either study agent, particularly for the duration of eight weeks only.

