7.2.4 Final Study Visit

Final Study Visit (Visit 2, Week 12 +/- 3 to 5 days)

- Record AE as reported by participant or observed by investigator
- Record participant's adherence to treatment regimen
- Record VAS scores for dyspareunia, itching, and dryness
- Record vital signs, results of physical exam including pelvic
- Collect pelvic samples for vaginal pH and vaginal tissue scraping for VMI
- Have patient fill out VSQ, FSFI, VSI, PGI-I
- Discuss the preliminary changes in their symptoms, if any exist
- Provide contact information for [name] to communicate any AE or side-effect experienced after the end of the study if patient believes it is related to the study

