7.2.5 Withdrawal/Early Termination Visit

If 12 weeks of study agent usage:

- Record AE as reported by participant or observed by investigator
- Record participant's adherence to treatment regimen
- Obtain GSM symptom history, and record VAS scores for dyspareunia, itching, and dryness
- Record vital signs, results of physical exam including pelvic
- Collect pelvic samples for vaginal pH and vaginal tissue scraping for vaginal maturation index
- Have patient fill out VSQ
- Discuss the obvious, preliminary changes in their symptoms, if any exist
- Provide contact information for [name] to communicate any AE or side-effect experienced after the end of the study if patient believes it is related to the study

If <12 weeks of study agent usage:

- Record AE as reported by participant or observed by investigator
- Record participant's adherence to treatment regimen
- Record vital signs, results of physical exam including pelvic
- Provide contact information for [name] to communicate any AE or side-effect experienced after the end of the study if patient believes it is related to the study

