10.3 Analysis Datasets

The analysis dataset will include the intent to treat cohort, to include all those randomized to treatment, as well as a per protocol set to include who used either the control or investigational product for at least 12 weeks.

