10.4 Description of Statistical Methods

Baseline (pre-randomization) participant demographics and clinical characteristics will be summarized through descriptive statistics overall, and by randomized group. Clinical characteristics will include past HRT use, uterus present or not, and components of their medical and gynecologic history. Details of each outcome measure is provided below. Analysis of the primary and secondary measures will include summarizing each by the mean and standard deviation at baseline and all measured time points, including at the primary outcome time of 12 weeks. For continuous measures, a linear mixed effects regression model will estimate the mean outcome at 12 weeks, both unadjusted and adjusted for baseline measurement. No further adjustment for participant characteristics is expected given the limited trial size. The linear mixed effects regression model will allow all participants to be included in analysis, regardless of completion of study follow up at 12 weeks, under the assumption of this assessment being missing at random.

Missing outcome data will be summarized by participant characteristics to understand how to better retain individuals in treatment.

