10.5 Sample Size

This study would be the first US-based randomized trial investigating HLA's usage for GSM treatment, to the authors' best knowledge. Thus, the sample size of 60 has been chosen to pilot the presented protocol, to assess feasibility and acceptability in quality of life for HLAs and to gather preliminary effectiveness for planning a larger effectiveness trial. The authors acknowledge the limitations of having enrolling 60 individuals, including generalizability. However in this initial stage of study implementation and design, expect this number to provide sufficient information.

No study to date has used the VSQ to assess the impact of treatment modalities for GSM, so there is no historical data to provide an assumed mean score. However, with 30 individuals randomized to each study treatment, we expect to have at least 80% probability of achieving a 95% confidence interval (CI) width of 1.7, assuming a standard deviation in the VLM of 2. With fewer individuals at any timepoint, the width of the CI will increase.

The assumed drop-out, withdrawal, cross-over and missing data rate is assumed to be 33%, which explains the enrollment goal of 60 to allow for 40 evaluable patients. This is a conservative estimate because the missing data rates in RCT's from four major journals has shown to be 20% or greater in about 18% of trials, which was also seen in quality-of-life studies (26, 27). We will monitor reasons for drop out and withdrawal of treatment to improve study adherence and follow up.

All participants will be included in the intent to treat analyses, and those participants who use the study intervention for at least 12 weeks will be included in the per-protocol analysis.

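### For women who leave the study with less than 12 weeks of product use, the only assessment list omits the VSQ, and the week-12 visit arranged for them names no assessments

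*Combined protocol and SAP*

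**What the plan says.** The primary endpoint is the change in VSQ from baseline to week 12 (4.2.1). There are two assessment times, Day 0 and week 12 (7.2.3, 7.2.4, Schedule of Events).

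- **7.2.4, Final Study Visit:** "Have patient fill out VSQ, FSFI, VSI, PGI-I", plus VAS, pH and VMI. Nothing makes these depend on how long product was used.
- **7.2.5, Withdrawal/Early Termination Visit:** after 12 weeks of use the list includes VAS, pH, VMI and VSQ. Under "If <12 weeks of study agent usage" it has adverse events, adherence, vital signs, examination and contact information only.
- **5.7.2:** for women who withdraw or are terminated, "a follow-up office visit will be set up at 12 weeks regardless of their participation". No assessments are named and 7.2.4 is not cited. If she refuses to attend, "a phone call will be made to discuss adverse events or unanticipated problems over the phone".
- **10.3:** the intent-to-treat cohort is "to include all those randomized to treatment".
- **10.4:** a linear mixed model includes women without week-12 follow-up "under the assumption of this assessment being missing at random".

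The Schedule of Events has no withdrawal column.

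**The concern.** The intent-to-treat estimate is meant to cover every randomised woman, but the only list written for women who leave with less than 12 weeks of use omits the endpoint being estimated. With no assessment between baseline and week 12, a woman without a week-12 VSQ gives the mixed model a baseline value and nothing about her response. The model then treats her as resembling women in the same arm with a similar baseline who were followed. That is doubtful if she left because of a side effect or because the product did not help her. The trial is also open label, so perceived benefit may affect who leaves.

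At stake are avoidable missing primary data, some loss of precision, and reliance on an assumption the data cannot test. The estimates are intended for planning a larger trial (10.1, 10.5), and a week-12 score that was not taken cannot be recovered later.

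**Working it through.** **1. Who is affected, from the text.**

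| Situation | Governing text | Week-12 VSQ taken? |
|---|---|---|
| Stops product, stays in study | 7.2.4; 7.2.6 decides on product and on study participation separately | Yes |
| Leaves study after 12 weeks of use | 7.2.5, first list | Yes |
| Leaves study with less than 12 weeks of use, attends at week 12 | 5.7.2 (content not stated); 7.2.5, second list (no VSQ) | Not stated |
| As above, will not attend | 5.7.2 phone call (safety only) | No |

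The gap is in the last two rows.

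**2. The plan's own figures (10.5).** Inputs: 30 women per arm, SD 2, 33% loss, and "at least 80% probability of achieving a 95% confidence interval (CI) width of 1.7". The SD is stated for VLM, a term the documents do not define; applying it to the VSQ is an assumption.

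Enrolment: 40/(1 − 0.33) ≈ 60, which agrees.

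For one arm's mean, the width at a sample SD of 2 is w = 2 × t(0.975, n−1) × 2/√n. The probability that the width is 1.7 or less is the chi-square distribution function with n−1 degrees of freedom at (n−1)(1.7/w)².

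| n per arm | w | P(width ≤ 1.7) |
|---|---|---|
| 30 | 1.49 | 0.87 |
| 25 | 1.65 | 0.62 |
| 22 | 1.77 | 0.43 |
| 20 | 1.87 | 0.32 |

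The n = 30 row agrees with the stated 80% or more, so the target is for one arm's mean with no missing data. For the between-arm difference at 30 per arm the probability would be only 0.03.

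The n = 20 row is the 33% loss the plan already expects. The rows for 22 and 25 show what follows if 2 or 5 of the 10 missing women per arm gave a week-12 VSQ. Those recovery numbers are assumptions; if none did, nothing is gained.

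**3. Illustrative bias.** Suppose k of 30 women in an arm leave early and would score δ points worse than the model predicts for them.

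- Error without their VSQ: (k/30)δ, making the arm look too good.
- Standard errors at 20 per arm: 2/√20 = 0.447 for an arm mean, 2√(2/20) = 0.632 for the difference.
- Error with their VSQ, if 10 of 30 were missing and the other 10 − k stay missing for unrelated reasons: kδ[1/(20+k) − 1/30]. The sign is now opposite, because early leavers are over-represented.

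| k, δ | Error without VSQ | In SE of arm mean | In SE of difference | Error with VSQ (opposite sign) |
|---|---|---|---|---|
| 1, 1 | 0.03 | 0.07 | 0.05 | 0.01 |
| 2, 2 | 0.13 | 0.30 | 0.21 | 0.05 |
| 3, 3 | 0.30 | 0.67 | 0.47 | 0.09 |

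Both k and δ are assumptions. The lower end is more likely, and the direction between arms is unknown.

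**The case against.** The strongest reply is that 5.7.2 and 7.2.5 describe different visits: a safety visit when the woman leaves, and a later visit at week 12. The only week-12 visit the protocol defines is Visit 2, which takes the VSQ. Omitting the VSQ from the earlier visit would then be sensible, since a score at week 4, say, is not the endpoint. This reading is tenable, so the two sections cannot be said to contradict each other. It does not close the gap: 5.7.2 never says its visit is Visit 2, and the only list addressed to these women has no efficacy items.

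A reader might also infer that any woman who stops product early loses her VSQ. The documents do not support that. Section 7.2.5 concerns leaving the study, and 7.2.6 separates the product decision from the study decision. The heading of the second list, worded by duration of use, leaves some ambiguity but no more.

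A reader might take the fall from 0.87 to 0.32 as the cost of this gap. It is not. It is the effect of the whole 33%, which pools drop-out, withdrawal, cross-over and missing data, and 10.5 already says that fewer women means a wider interval.

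Finally, this is a pilot that does not focus on formal comparison (10.1). It states its missing-data assumption, summarises missingness by participant characteristics (10.4) and tabulates reasons for discontinuation (10.4.4). These steps describe the missing data. They do not supply the missing scores.

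**Conclusion.** The point holds for women who withdraw or are terminated with less than 12 weeks of product use. The protocol may bring them in at week 12 without collecting the primary endpoint, leaving the intent-to-treat result for them to rest on the missing-at-random assumption. The gap in the text is certain; its effect is not. The number of such women, their attendance and their scores are not given, and 20 of 60 is an upper bound rather than a forecast. On the illustrative inputs the bias is at most about 0.3 points, with a residual of at most about 0.09 in the other direction once their scores are collected. The change should be made because the data are cheap to obtain at a visit already planned, not because a large error has been shown.

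**What to change.** - In 5.7.2, state that the week-12 visit follows 7.2.4 for every woman who has not withdrawn consent to follow-up: at minimum VSQ, VSI, FSFI and VAS, with pH and VMI where clinically appropriate.
- In the less-than-12-weeks list of 7.2.5, add a cross-reference to that sentence.
- State that these values enter the intent-to-treat analysis and that the per-protocol set is unchanged.
- Optionally, offer the VSQ by phone to those who will not attend and record the mode. Staff would know the treatment arm, and the documents say nothing about phone administration, so this is a fallback only.

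Sections 5.7.1 and 7.2.6 need no change. The cost is a few lines of wording, a few minutes at a planned visit, some week-12 values taken off product and, if the phone option is used, one CRF field. Off-product values are appropriate for an intent-to-treat estimate.

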7.2.6 Unscheduled Visit

- Obtain patient's reason for visit
- Perform relevant physical exam
- Based on the clinical context, determine whether study agent should be continued or discontinued or modified
- Discuss plan with patient
- Based on the clinical context, document whether patient will continue in study or be removed

CONFIDENTIAL

This material is the property of the NYU School of Medicine and Langone Medical Center. Do not disclose or use except as authorized in writing by the study sponsor
Interventional Template Version: 11 January 2019

Concomitant Medications, Treatments, and Procedures

All concomitant prescription medications taken during study participation will be recorded on the case report forms (CRFs). For this protocol, a prescription medication is defined as a medication that can be prescribed only by a properly authorized/licensed clinician. Medications to be reported in the CRF are concomitant prescription medications, over-the-counter medications and non-prescription medications.

Prohibited Medications, Treatments, and Procedures

Treatment with systemic HRT will not be permitted during or within 6 weeks of starting this study.

Participant Access to Study Agent at Study Closure

HLA is an over the counter medication so patients will have access to the study agent after closure. However, the cost will not be covered after study closure and will be the subject's responsibility, so purchasing the study agent may be cost prohibitive.

8 Assessment of Safety

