5.2 Exclusion Criteria

An individual who meets any of the following criteria will be excluded from participation in this study:

1. Use of any HRT (systemic or local) or raloxifene within six weeks of proposed start date
2. History of estrogen-sensitive tumor
3. Undiagnosed vaginal bleeding in the past 12 months
4. History of thromboembolic event
5. Currently have or have had liver problem
6. Bleeding disorder
7. Impaired mental status
8. Prior pelvic irradiation
9. Active vaginal infection
10. Any medical reason the investigator deems incompatible with treatment with vaginal estrogen

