5.7 Participant Withdrawal or Termination

5.7.1 Reasons for Withdrawal or Termination

Participants are free to withdraw from participation in the study at any time upon request. An investigator may terminate participation in the study if:

- Any clinical adverse event (AE), laboratory abnormality, or other medical condition or situation occurs such that continued participation in the study would not be in the best interest of the participant
- The participant meets an exclusion criterion (either newly developed or not previously recognized) that precludes further study participation

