6.2 Study Agent Accountability Procedures

NYU Investigational pharmacy will be used to ensure the drug and device are stored and dispensed in a regulated manner through the faculty group practice study site. Unused product will be returned to JDS Therapeutics ([name]). Both medications will be stored at the office in a locked cabinet. There will be no additional interventions.

Regular study drug reconciliation will be performed to document drug assigned, drug consumed, and drug remaining. This reconciliation will be logged on the drug reconciliation form, and signed and dated by the study team.

7 Study Procedures and Schedule

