7.1 Study Procedures/Evaluations

7.1.1 Study Specific Procedures

- Medical history: will be obtained by interview
 - Included: genitourinary symptoms
- Medication history:

CONFIDENTIAL

This material is the property of the NYU School of Medicine and Langone Medical Center. Do not disclose or use except as authorized in writing by the study sponsor
Interventional Template Version: 11 January 2019

- All history of HRT use currently or in the past
 - Any usage of HRT in the last six weeks would prohibit participation until six weeks off HRT
- Physical Exam:
 - Pelvic:
 - Vaginal pH sample
 - Vaginal tissue sample via scraping for VMI
- VSQ, FSFI, VSI
- Counseling on usage of medication depending on the study arm randomization
- Patient report of medication compliance at twelve week follow-up

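### The on-study hormone prohibition names only systemic HRT, so a woman on HLA could add non-study vaginal estrogen and still count as per-protocol

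*Combined protocol and SAP*

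**What the plan says.** Three parts of the plan bear directly on this.

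- **Entry.** Section 5.2 excludes "Use of any HRT (systemic or local) or raloxifene within six weeks of proposed start date".
- **During the study.** The unnumbered Prohibited Medications, Treatments, and Procedures text, which follows 7.2.6, reads: "Treatment with systemic HRT will not be permitted during or within 6 weeks of starting this study". It mentions neither local estrogen nor raloxifene.
- **Analysis sets.** Section 10.3 describes "a per protocol set to include who used either the control or investigational product for at least 12 weeks", and 10.5 repeats that "those participants who use the study intervention for at least 12 weeks will be included in the per-protocol analysis". Neither places a condition on other treatment. The 10.3 wording does not require the product to be the assigned one.

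Other text touches the point:

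- Section 5.7.1 lets the investigator end participation when "The participant meets an exclusion criterion (either newly developed or not previously recognized) that precludes further study participation".
- Section 7.1.1, under medication history, says "Any usage of HRT in the last six weeks would prohibit participation until six weeks off HRT".
- Section 6.2 closes its paragraph on storage with "There will be no additional interventions".
- Section 10.5 says "The assumed drop-out, withdrawal, cross-over and missing data rate is assumed to be 33" per cent, so it counts cross-over within the planned loss.
- The Concomitant Medications text has prescription and non-prescription medicines recorded on the case report form (CRF).

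**The concern.** The stated aim in 10.1 is to estimate outcomes in the HLA arm, to inform a larger trial. Vaginal estrogen is both the comparator and, according to 2.1, the usual next step when moisturizers fail. The trial is open label (10.6.1), so a woman on HLA whose symptoms persist knows she is not receiving estrogen. Section 10.4.5.1 schedules no formal visit between baseline and week 12.

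If she adds vaginal estrogen, her week-12 values reflect HLA plus estrogen. The endpoints most directly exposed are vaginal pH and squamous-cell percentage, which 4.2.2 and 10.4.2 treat as markers of hormonal influence. The intent-to-treat set keeps her by design. The per-protocol set is where a reader would look for HLA used alone, yet its definition does not remove her.

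**Working it through.** **Comparing the texts.** The question is whether any rule stops a woman who uses HLA for 12 weeks and adds non-study vaginal estrogen from counting as per-protocol.

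- 5.2 covers local HRT, but its window is tied to the proposed start date, so use after randomization does not literally meet it.
- The Prohibited Medications sentence covers the study period, but only for systemic HRT.
- 5.7.1 is discretionary and refers back to the exclusion criteria. If add-on use is first found at week 12, she has already completed 12 weeks of product, so termination would not change her per-protocol status.
- 7.1.1 looks back over HRT history; the Schedule of Events lists medication history at Visit 1 only.
- The 6.2 line is a general remark within drug accountability.
- 10.5 mentions cross-over but neither defines it nor ties it to an analysis set.
- The concomitant-medication record exists, but no analysis rule uses it.

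She therefore meets both statements of the per-protocol definition.

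**The plan's own figures.** Inputs from 10.5: 40 evaluable, 33% loss, 30 per arm, SD 2, 95% CI width 1.7 with at least 80% probability.

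- Enrollment: 40 / (1 − 0.33) = 59.7, rounded up to 60. This matches.
- Single-arm width = 2 × t(0.975, n−1) × SD / √n. At n = 30 the formula gives 1.49. Allowing for sampling variation in the SD, the 80th percentile is 1.64 and the probability of a width of at most 1.7 is 0.87. This agrees with the plan.

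**Size of the shift in the HLA-arm VSQ mean.** Assumptions: k add-on users among n women, each differing by d = 2 points from her own value on HLA alone. Two points is one SD in 10.5; the plan attaches that SD to an undefined abbreviation, VLM, taken here to mean VSQ. The documents give neither k nor d.

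Shift = d × k / n. Half-width = t(0.975, n−1) × 2 / √n.

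| n per arm | Half-width | k = 1 | k = 2 | k = 3 |
|---|---|---|---|---|
| 20 (40 evaluable, split equally) | 0.936 | 0.10 (10.7%) | 0.20 (21.4%) | 0.30 (32.1%) |
| 30 (all randomized) | 0.747 | 0.07 (8.9%) | 0.13 (17.9%) | 0.20 (26.8%) |

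Percentages are of the half-width.

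A wider range, with 5% to 20% users (1 to 4 of 20) and d from 1 to 3 points, gives shifts from 0.05 × 1 = 0.05 to 0.20 × 3 = 0.60 point. That is 5% to 64% of 0.936. The top end needs one woman in five to add estrogen and each to differ by 1.5 SD.

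**Hormone markers.** Section 4.2.2 gives pH 6.0 to 8.0 after menopause and 3.5 to 4.5 when estrogenized, so a full move between the ranges is 6.0 − 4.5 = 1.5 to 8.0 − 3.5 = 4.5 units. One such user among 20 shifts the mean by 1.5/20 = 0.075 to 4.5/20 = 0.225 units. This is an upper-end illustration. The documents give no SD for pH or squamous-cell percentage, so neither can be set against its precision.

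**The case against.** The strongest reply is that the plan never intended add-on estrogen to be acceptable. The word systemic has an innocent explanation: local estrogen is the control treatment, so a blanket on-study ban would have contradicted one arm. Section 4.1 describes two regimens, and HLA plus estrogen is neither. Counting cross-over in the loss that leaves 40 evaluable suggests such women were not meant to be evaluable. Staff can remove a woman under 5.7.1 or after an unscheduled visit (7.2.6). Section 14.3 leaves further detail on deviations to a Manual of Procedures that is not among these documents.

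Much of this stands as evidence of intent. A reader might infer that the protocol deliberately permits local estrogen during treatment, or has no safeguard at all; the documents support neither. But these provisions are discretionary, general or undefined, and none is a per-protocol rule.

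It is also true that little rests on the per-protocol set. This is an estimation pilot, formal comparison is not its focus, the mixed model in 10.4 includes all participants, and no test or decision is assigned to per-protocol.

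Finally, excluding add-on users has a cost. They may often be the women for whom HLA is not working, and removing them could make the per-protocol HLA result look better than it is. That stands, and it shapes the fix.

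**Conclusion.** The gap is real but modest. The on-study prohibition is narrower than the entry criterion, and the per-protocol definition does not make up the difference.

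A reader might go further and infer that the primary result is materially biased. The documents do not support that. They give no rate of outside estrogen use, and with 1 to 3 users of 20 at 2 points each the HLA-arm VSQ mean moves 0.10 to 0.30 point, at most about a third of the half-width of 0.94. One user has a small effect. Only the far corner of the assumed range, four users of 20 at 3 points each, approaches two thirds of the half-width. For pH and squamous-cell percentage the exposure is more direct, but its relative size cannot be stated.

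The conclusion about the wording rests on the text alone; every figure for its effect rests on assumed values of k and d, and on reading the SD of 2 as that of VSQ. The change is worth making because it is cheap and protects the quantity the pilot sets out to estimate.

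**What to change.** **Main change.** Reword the Prohibited Medications sentence so that systemic HRT, local HRT and raloxifene, other than the assigned study product, are all barred from six weeks before the start until the end of the 12 weeks. The carve-out keeps the control arm valid, and the scope then matches 5.2.

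**Secondary change.** In 10.3, define per-protocol as at least 12 weeks of the assigned product without non-assigned estrogen, identified from the concomitant-medication CRF, and carry this into 10.5. Keep these women in the intent-to-treat set. Report the number of add-on users by arm, so that a reader can judge how far their exclusion favors HLA. That count is also useful to a pilot of acceptability.

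**Cost.** One reworded sentence, one added condition and one reported count, with no new data collection required. The per-protocol set may lose a few women, with the selection risk described above. The Visit 2 lists in 7.2.4 and the Schedule of Events show no concomitant-medication check, so a single HRT question at that visit would be a sensible, optional addition.
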